6.6 Pharmacokinetics (PK) Population

The PK Population includes all subjects enrolled in the PK Substudy who provide concentration data for at least one sample.

The PK Population will be used for all PK analysis described in Section 9.8.

7.0 Interim Analyses

There are no planned interim analyses for this study.

8.0 Data Review

8.1 Data Handling and Transfer

Processes for data handling and transfer will be documented in the Data Management Plan.

8.2 Data Screening

Beyond the data screening built into the PRA Data Management Plan, the PRA programming of analysis datasets, tables, figures, and listings (TFL) provides additional data screening. Presumed data issues will be output into SAS logs identified by the word "Problem" and extracted from the logs by a SAS macro and sent to Data Management.

Review of a pre-freeze TFL run on clean subjects and a post-freeze TFL run on the frozen database allow for further data screening prior to lock. The post-freeze TFL will be discussed with the sponsor in a data review meeting to identify any final data issues and seek corrections prior to database lock. The PRA statistician and the sponsor must approve database lock.

8.3 Data Review Meetings

Data review meetings will be held during the course of the study prior to database lock and the following may be reviewed during these meetings:

- Important protocol deviations and exclusion from the PP Population
- Classification of at-risk and not at-risk cycles for the Pearl Index derivation where the classification is not clear based on the data collected and the rules in the SAP
- Classification of on-, pre- and post- treatment pregnancies for the Pearl Index derivation
- Classification of method failure and user failure pregnancies for the method failure Pearl Index derivation
- Classification of evaluable and non-evaluable cycles for the PP bleeding analysis where the classification is not clear based on the data collected and the rules in the SAP

9.0 Statistical Methods

All analyses will be conducted using SAS version 9.4 or higher.

No formal statistical analyses will be performed in this study.

The following conventions will be used when presenting summary statistics for study data:

- Continuous variables will be summarized using the following descriptive statistics: number of subjects (n), mean, standard deviation (SD), standard error of the mean (SEM), median, minimum (min), maximum (max), 25th percentile (lower quartile or Q1) and 75th percentile (upper quartile or Q3)
- Categorical and count variables will be summarized by the number of subjects (n) and the percent of subjects in each category. For AE tables, m may also be presented which represents the number of events. Percentages will be presented to 1 decimal place

- The number of subjects or observations will be presented as an integer
- Mean, median, lower quartile and upper quartile will be presented to 1 decimal place more than the raw value
- Min and max will be presented to the same number of decimal places as the raw value
- Standard deviation will be presented to 2 decimal places more than the raw value, up to a reasonable number of decimal places (i.e., rarely more than 3 decimal places unless the nature of the data suggests this)
- The denominator for percentage calculations will be the number of non-missing observations at that visit. Where this isn't appropriate, the number of subjects in the relevant population will be used

9.1 Subject Disposition

All summaries in this Section will be presented for subjects aged 16 to 35 years and for all subjects. This will be based on the Screened Population.

The number and percentage of subjects treated in the study will be presented, together with the number and percentage of subjects who completed the study and the number and percentage of subjects who withdrew from the study prematurely with a breakdown of the corresponding reasons for withdrawal. If a subject returns all study medication that was dispensed, then the subject will not be classed as treated. If there is at least one pill that was dispensed but was not returned, but the subject diary has no pills recorded as taken, then it will be assumed that the subject has not taken any study medication and will not be classed as treated. However, if the subject has no pills taken according to the diary but the subject has a pregnancy that is classified as either an on-treatment or post treatment pregnancy based on the Principal Investigator's assessment in the pregnancy narrative, then the subject will be classed as treated. In the case of missing diary data, it will be assumed that no pills were taken for the corresponding days with missing data. If there was at least one pill that was dispensed but was not returned and the subject has taken at least one pill according the subject diary, then that subject will be classed as treated.

Tabulations of the number and percentage of subjects included in each analysis set will be provided. The percentage will not be presented for the Screened and Enrolled Populations. Percentages will be derived based on the number of subjects enrolled.

A tabulation of the number and percentage of subjects enrolled at each site and country will be summarized in the Enrolled Population.

Disposition data and the site and country will be listed in the Enrolled Population. Information on inclusion in each of the analysis sets will be listed in the Screened Population. Screening failures will be listed with the reason for the screening failure.

The cumulative discontinuation rate, as determined by life-table methods, together with the corresponding 95% CIs will be presented in the ITT population for all subjects and for subject's aged 16 to 35 years inclusive at Screening. The life-table analysis will evaluate the cumulative probability of discontinuation from the study by cycle using PROC LIFETEST in SAS where the time variable is the cycle where the discontinuation occurred for subjects who discontinued from the study prematurely. Subjects who did not discontinue from the study prematurely will be censored in Cycle 13. The rate of discontinuation and 95% CIs will be calculated based on Kaplan-Meier estimates for each cycle. Additionally, the estimated survival function against time (cycle) will be provided.

9.2 Protocol Deviations and Violations

The important protocol deviations for this study will be specified in the Protocol Deviation Guidance Template. Per PRA processes, protocol deviations will be entered into PRA's Clinical Trials Management System (CTMS). The study team and the sponsor will conduct ongoing reviews of the protocol deviations from CTMS to identify deviations which meet the criteria for important.

The number and percentage of subjects who had an important protocol deviation will be summarized in the ITT Population.

All important protocol deviations will be listed in the ITT Population.

The important protocol deviations will be reviewed and their potential to impact the analysis of the bleeding data will be assessed against the rules specified in Sections 5.1.2. If there is a potential for a specific important protocol deviation to impact this analysis, then the impacted cycles for that subject will be excluded from the PP analysis for bleeding data. Subjects with no evaluable cycles will be excluded from the PP population for the analysis of bleeding data. The PP Population and the cycles to be excluded from the PP analysis must be finalized at the post-freeze data review meeting (or earlier), prior to database lock.

9.3 Treatments

All summaries described in this Section will be presented for subjects aged 16 to 35 years and for all subjects in the Safety Population.

9.3.1 Extent of Study Drug Exposure

The overall duration of total exposure and actual exposure will be summarized using descriptive statistics. In addition, the total extent of exposure and total extent of actual exposure across all subjects will be summarized in years.

Additionally, the number and percentage of subjects exposed for at least 26 weeks and at least 52 weeks based on actual exposure will be presented. The denominators for calculating the percentages will be based on the number of subjects.

The number of cycles as defined in Section 5.1 will also be summarized using descriptive statistics. The number and percentage of subjects who had at least 1, 2, 3, etc. cycles will be summarized.

Exposure data will be listed for all subjects in the Safety Population.

9.3.2 Treatment Compliance

Treatment compliance by cycle and overall will be summarized using descriptive statistics including the following information:

- The number of pills taken
- The compliance

The number and percentage of subjects missing no pills, 1 pill, 2 pills and more than 2 pills will be summarized for each cycle where the cycle is defined as per Section 5.1. The denominator will be the number of subjects in the Safety Population who started that cycle.

The total number of pills taken across all subjects will be presented. Compliance data will be listed for all subjects in the Safety Population. Drug accountability data will be listed only in the Safety Population.

9.3.3 Prior, Post-Study Treatment and Concomitant Medications

Medications received prior to or concomitantly with study drug, categorized by preferred term according to WHODRUG Jun 2017 will be summarized in the Safety Population. The number and percentage of subjects using each medication will be displayed. This will be repeated for prior medications.

All prior, post-study treatment and concomitant medications will be listed in the Safety Population.

9.4 Demographic and Baseline Characteristics

All summaries described in this Section will be presented for subjects aged 16 to 35 years and for all subjects.

The following demographic data and baseline characteristics will be summarized in the ITT and PP Populations:

- Age at Screening
- Age group (≥16 to ≤25 years, >25 to ≤35 years, >35 to ≤50 years) at Screening
- Highest education level
- Ethnicity
- Race
- Height
- Weight at Baseline
- BMI at Baseline
- BMI categories (<30kg/m², ≥30kg/m²) at Baseline

If subjects record more than one race, then for the summary table, these subjects will be included in the Other Race group. BMI will be derived programmatically from the height and weight collected.

The subject's previous contraceptive method used will be summarized in terms of the number and percentage of switchers, starters and true new users in the ITT Population. Note: subjects who are true new users are a subset of the starters.

The following information will be summarized for gynecological history in the ITT Population:

- Gravidity and parity status
- Menstrual cycle length for starters
- Dysmenorrhea
- Previous contraceptive method used
- History of pregnancy during accurate hormonal contraceptive use

Smoking status, including the following information for current smokers will be presented in the ITT Population:

- The number of days per week where the subject smokes
- The number of tobacco products per day that the subject smokes

All demographic data, baseline characteristics, gynecological history, contraceptive use and smoking status will be listed in the ITT Population. In the demography listing, if a subject has more than one race recorded, then all races selected will be listed for that subject.

Medical history will be summarized in the ITT. Medical history will be classified into a standardized terminology using the Medical Dictionary for Regulatory Activities (MedDRA) system organ classifications and preferred terms. Version 20.0 of MedDRA will be used as coding dictionary.

Surgical history will not be summarized.

All medical and surgical history recorded will be listed in the ITT Population.

9.5 Efficacy Analyses

9.5.1 Primary Variable

The primary variable will be summarized using the Pearl Index in the ITT population aged 16 to 35 years inclusive at Screening with at-risk cycles. Subjects in this age group will not be censored on their 36th

birthday for the pregnancy assessment. The Pearl Index will be presented with corresponding 95% Cls. No formal statistical analyses will be conducted for the primary variable.

The Pearl Index, defined as the number of pregnancies per 100 women-years of treatment, will be calculated as

1300 x number of on – treatment pregnancies

Pearl Index = $\frac{1}{\text{number of women} - 28 \text{ day equivalent cycles of treatment}}$

Only at-risk cycles will be included in the denominator of the Pearl Index calculation. At-risk cycles will be defined as cycles in which the following criteria are met:

- 1. No other methods of birth control (including condoms and emergency contraception) are used by the subject as confirmed in the subject diary
- The subject confirmed that sexual intercourse occurred during the cycle in the subject diary

Note that if conception occurs in a cycle, then that cycle will be included as an at-risk cycle in the denominator even if other methods of birth control were used during that cycle or the subject did not confirm that they had had sexual intercourse. Cycles after the cycle of conception will not be included as at-risk cycles and will be excluded from the denominator.

The number of women-28 day equivalent cycles of treatment is the sum of the number of at-risk cycles across all subjects. The total number of at-risk cycles will be presented in the table.

All on-treatment pregnancies will be included in the numerator for the Pearl Index (see Section 5.9.1 for definition of on-treatment pregnancies).

For calculation purposes a cycle will be defined as per Section 5.1.1.

The 95% CI for Pearl Indices will be calculated using a Poisson distribution. The confidence interval limits are calculated by the following equations:

$$CI_{LOWER} = 1300 \times \frac{\frac{1}{2}\chi^2_{0.025; 2x}}{the number of women - 28 day equivalent cycles of treatment}$$

$$CI_{UPPER} = 1300 \times \frac{\frac{1}{2}\chi^2_{0.975; 2(x+1)}}{\text{the number of women} - 28 \, day \, equivalent cycles of treatment}$$

where x is the number of on-treatment pregnancies.

The Pearl Index and corresponding 95% CIs will be presented by the subgroups described in Section 4.3 for subjects aged 16 to 35 years. All subject diary data, pregnancy information and at-risk cycles for each analysis will be listed.

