- 37. History of alcohol or drug abuse (including laxatives) within 12 months prior to screening.
- 38. Any prior procedure, disease or condition that could result in altered absorption, excessive accumulation, impaired metabolism, or altered excretion of the investigational product.
- 39. Uncontrolled thyroid disorders.
- 40. Participation in another investigational drug clinical study within 1 month (30 days) or have received an investigational drug within the last 3 months (90 days) prior to study entry. Subjects who participated in an oral contraceptive clinical study, using FDA/EU approved active ingredients, may be enrolled 2 months (60 days) after completing the preceding study.
- 41. Sponsor, the Contract Research Organization (CRO) or Investigator's site personnel directly affiliated with this study.
- 42. Is judged by the Investigator to be unsuitable for any reason.

Investigational Product; Dose; and Mode of Administration:

The investigational product is a 15 mg E4/3 mg DRSP tablet administered orally once daily in a 24/4-day regimen (i.e. 24 days of active tablets followed by 4 days of placebo tablets).

Duration of the study:

Overall treatment duration is up to thirteen 28-day cycles, i.e., 12 months.

Those subjects who discontinue due to a pregnancy wish will be followed-up for a maximum of one year after study discontinuation for return of spontaneous menstruation and until pregnancy or initiation of a contraceptive method (whichever occurs first).

Statistical Methods:

For the efficacy analyses, the pregnancy rates will be expressed as:

- Pearl Index (number of pregnancies per 100 woman years due to method and user failure) with a two-sided 95% confidence interval (CI);
- Method failure Pearl Index (number of pregnancies per 100 woman years due to method failure only) with a two-sided 95% CI;
- Life-table analysis (cumulative pregnancy rate).

For Pearl index calculations, thirteen 28-day cycles constitute one woman-year.

Primary Efficacy Analysis:

Pearl Index for subjects aged 16 to 35 years, inclusive, at the time of screening.

Secondary Efficacy Analyses:

- Method failure Pearl Index and life-table analysis for subjects aged 16 to 35 years, inclusive, at the time of screening.
- Pearl Index, method failure Pearl Index and life-table analysis for the overall study population (16 to 50 years).

Additional Summaries:

- Occurrence of scheduled and unscheduled vaginal bleeding/spotting in the overall study population.

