12.1 Determination of Sample Size

Sample size is based on needing a sufficient number of cycles such that the difference between the Pearl Index and the upper limit of the two-sided 95% confidence interval (CI) for the Pearl Index does not exceed 1. Assuming that the true Pearl Index is 1.0 and that a Poisson model is used to derive the CIs, then at least 12,337 at risk cycles are required for a power of 90% in the 16 to 35 year old population.⁸ If a not at risk cycle rate of 20% and a dropout rate of approximately 45% (assuming that we have an average of 4 cycles for subjects that discontinue) are assumed, approximately 1800 16 to 35 year old subjects need to be enrolled and initiate the investigational product. Additionally, it is planned for a maximum of 200 subjects > 35 years to be enrolled and initiate the investigational product. Therefore, in total, approximately 2000 subjects will be enrolled in the study and initiate the investigational product. Additionally, a subset of approximately 500 subjects will be enrolled in the PK Substudy.

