12.4 Efficacy Analyses

The efficacy analysis will be based on the Pearl Index. The Pearl Index, defined as the number of pregnancies per 100 women-years of treatment, will be calculated as

 $Pearl Index = \frac{1300 \times \text{number of on} - \text{treatment pregnancies}}{\text{number of women} - 28 \text{ day equivalent cycles of treatment}}$

Only at risk cycles, i.e. cycles in which no other methods of birth control (including condoms) are used and during which the subjects confirmed that sexual intercourse has occurred, will be included in the denominator of the Pearl Index calculation. The subject diary data will be used to determine whether additional birth control methods were used and whether the subject has had intercourse.

Note that if conception occurs in a cycle, then that cycle will be included in the denominator even if other methods of birth control were used during that cycle or the subject did not confirm that they had had sexual intercourse. Cycles after the cycle of conception will be excluded from the denominator. All on-treatment pregnancies will be included in the numerator for the Pearl Index.

On-treatment pregnancy is defined as pregnancy with an estimated date of conception within the on-treatment period, i.e. Day 1 to 7 days after the intake of investigational product (whether active or inactive tablet). In cases where the date of conception cannot be established unequivocally (e.g. subjects is lost to follow-up), this pregnancy will be considered an on-treatment pregnancy. For calculation purposes a cycle will be defined as 28 days.

The method failure Pearl Index is calculated using the same method as the Pearl Index, but includes only those pregnancies that were classified as method failure and not pregnancies due to user failure, i.e. incorrect intake of the contraceptive product. Compliance data will be used to determine if the pregnancy was due to user failure.

Each on-treatment pregnancy will be reviewed and classified as either a method failure or a user failure pregnancy prior to database lock. Pregnancies will only be designated as user

failures if there is documentation that the subject did not use the test article correctly during the treatment cycle the conception occurred, including the instructions to be followed in case of missed pill(s).

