5.0 Definitions

5.1 Cycle

The expected duration of a cycle is 28 days. A 28-day cycle consists of 24 days of active tablet intake followed by 4 days of inactive tablet intake and subjects who complete the study are expected to have completed thirteen 28-day cycles.

All cycles will be determined using the start dates recorded in the diaries. The first day of a cycle is the start date recorded on the diary for that cycle and the last day of a cycle coincides with the day before the start date recorded on the diary for the next cycle. However, because the last cycle of use has no start date for a following cycle, the last day of the cycle will be assumed to be the date of last dose of study medication, whether this is an active or inactive tablet. The date of last dose of study medication in the last cycle will be derived from the data collected in the diary.

If the conception is confirmed to be during a specific cycle in the narrative and this cycle is not in the diary data, then the cycle will be included as cycle in the exposure for the derivation of the Pearl Index. If the cycle in which conception occurred is not known, cycle(s) up to the one in which the positive pregnancy test occurred will be included in the exposure for the derivation of the Pearl Index.

For the analysis of bleeding data, the cycle will be shifted by 3 days with the 3 days of the next cycle included in the previous cycle. For example, in the bleeding analysis Cycle 2 will be from Day 4 of Cycle 2 to Day 3 of Cycle 3 inclusive.

The start and stop times of a cycle will be determined before determining whether the cycle is evaluable for the Pearl Index or evaluable for the bleeding data. Data review meetings may be held to determine if cycles are at-risk cycles for the Pearl Index and if they are evaluable for the bleeding analysis prior to database lock (see Section 8.3) if the classification is not clear from the data collected and the rules in the SAP.

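### The Pearl Index denominator counts a discontinuer's partly used last pack as a full 28-day cycle, a small overstatement of exposure that the SAP should resolve with a days/28 rule

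*SAP*

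**What the plan says.** - **Unit.** The Pearl Index formula (Protocol 12.4, SAP 9.5.1) divides by women-28 day equivalent cycles. The Protocol synopsis says that "thirteen 28-day cycles constitute one woman-year", and Protocol 12.4 adds: "For calculation purposes a cycle will be defined as 28 days".
- **Counting rule.** SAP 9.5.1 makes the unit operational: the number of women-28 day "equivalent cycles of treatment is the sum of the number of at-risk cycles across all subjects". For the definition of a cycle it refers to SAP 5.1.1. That section gives the at-risk criteria but, for the primary index, no length limit and no conversion of days to cycles.
- **Cycle ends.** Under SAP 5.1, "the last day of a cycle coincides with the day before the start date recorded on the diary for the next cycle". For the final cycle, "the last day of the cycle will be assumed to be the date of last dose of study medication".
- **At-risk criteria (SAP 5.1.1).** No other birth control, and intercourse confirmed in the diary for that cycle. SAP 5.15.1 drops a cycle in which either answer is missing.
- **Numerator window.** SAP 5.3 counts conceptions up to 7 days after the last dose as on-treatment. SAP 5.9.2 assigns them to the cycle of the last dose.

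**The concern.** A woman who stops on Day 3 of a pack, having reported intercourse and no other method, contributes 3 days of use. The denominator credits her with 28. The formula asks for 28-day equivalents, and a plain count is equivalent only when every cycle lasts 28 days.

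Other parts of the SAP do deal with short or interrupted cycles. The per-protocol bleeding analysis drops cycles under 22 days (SAP 5.1.2). By-cycle compliance uses days to last dose (SAP 5.7.1). The life table censors a discontinuer one cycle before she stops (SAP 9.5.2.3), so it gives no credit for the cycle that the Pearl Index credits in full. SAP 5.15.5.2 even works an example in which the last tablet is taken on Day 4 of Cycle 1, and it sends Cycle 1 to the denominator under the 5.1.1 rules.

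The method-failure indices share the problem. Days after the last tablet lie outside the cycle, so the missed-pill criteria (5 and 6 in SAP 5.1.1) cannot register them. A three-day last cycle with its tablets taken can pass as compliant.

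At stake is a small downward bias in the primary estimate of a single-arm trial that has no comparator to absorb it.

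**Working it through.** **Inputs from Protocol 12.1 and SAP 3.1.** 1,800 women aged 16 to 35; 45% dropout; 13 cycles per completer; 4 cycles on average per discontinuer; 80% of cycles at risk; true Pearl Index 1.0; 12,337 at-risk cycles required.

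**Plan's figure reproduced.** Precision is met when the upper Poisson limit minus the index is at most 1, that is, when chi-square(0.975; 2(x+1))/2 − x ≤ N/1300. With x Poisson of mean N/1300, the smallest N from which the probability stays at or above 90% is 12,337 (0.940 there, 0.899 at 12,336). This matches the plan.

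**Planned denominator.**
- Completers: 1,800 × 0.55 = 990. Discontinuers: 1,800 × 0.45 = 810.
- At-risk cycles: 0.8 × (990 × 13 + 810 × 4) = 0.8 × 16,110 = 12,888.
- Of these, discontinuers' last cycles: 810 × 0.8 = 648.

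**Excess.** Excess cycles = 648 × (mean uncredited days)/28. The ratio of the pro-rated index to the counted index = 12,888/(12,888 − excess). The documents give no distribution of stop days, so the second column is an assumption in every row.

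| Last cycle ends at | Stop day assumed | Mean uncredited days | Excess cycles | Cycles left | Index ratio |
|---|---|---|---|---|---|
| Last dose | Uniform, Days 1–28 | 13.5 | 312 | 12,576 | 1.025 |
| Last dose + 7 days, capped at Day 28 | Uniform, Days 1–28 | 7.5 | 174 | 12,714 | 1.014 |
| Last dose | Half finish the pack, half uniform | 6.75 | 156 | 12,732 | 1.012 |
| Last dose | All stop on Day 27 | 1 | 23 | 12,865 | 1.002 |
| Last dose | All stop on Day 1 | 27 | 625 | 12,263 | 1.051 |

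The 7.5 days in the second row is the mean of max(0, 21 − d) over d = 1 to 28, which is 210/28. If every discontinuer finishes her pack, the excess is zero.

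**Meaning of the planned mean of 4.** If it already denotes pro-rated cycles, a half-pack excess gives a count of 0.8 × 1,800 × (0.55 × 13 + 0.45 × 4.5) = 13,212 against a true 12,888. The excess is again 2.5%.

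**Against sampling error.** With 10 pregnancies, the index on 12,888 cycles is 1.01 (95% limits 0.48 to 1.86). On 12,714 cycles it is 1.02 (0.49 to 1.88), and on 12,576 it is 1.03 (0.50 to 1.90).

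**Offset from long cycles.** A cycle ends the day before the next pack starts, so a gap between packs lengthens it, yet it still counts as one. The uniform-stop excess is 648 × 13.5 = 8,748 days, or 8,748/12,888 = 0.68 day per at-risk cycle. With the 7-day credit it is 4,860/12,888 = 0.38 day. A net average overrun of that size would cancel the effect. Short cycles within treatment work the other way: SAP 5.7.1 describes a pack started on Day 25 of the previous one, and that 24-day cycle also counts as one. The documents give no data on either.

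**The case against.** - **Declared convention.** The protocol's 28-day sentence can mean that each cycle is valued at 28 days, which is what the SAP does. Other contraception and intercourse are recorded per cycle, and cycles are included or excluded whole. This stands in part: the SAP does not plainly contradict the protocol. It does leave the word equivalent without effect for a cycle of 3 days.
- **Numerator window.** Conceptions within 7 days of the last dose count, so part of the rounded-up time is time in which a pregnancy would be counted. This stands, and it is why the 1.4% figure sits beside the 2.5%. It reduces the excess without removing it.
- **At-risk filter.** A pack of a few days leaves less time for intercourse to be confirmed, missing answers exclude the cycle, and women planning to stop may be given another method. The 80% rate is therefore probably too high for last packs, and 648 with it.
- **Shortfall against the target.** A reader might infer that the trial could fall below its 12,337 cycles. The documents do not support that. It would need a loss of 12,888 − 12,337 = 551 cycles, or 551 × 28/648 = 23.8 uncredited days on average in every at-risk last pack, with no credit for the 7-day window. With that window credited, even a stop on Day 4 by every discontinuer leaves 12,888 − 648 × 17/28 = 12,495. The figure is also a planning number and not a success criterion.
- **Small, descriptive and recoverable.** SAP 9.5.1 plans no formal test, sets no threshold, and lists the at-risk cycles and diary data. This stands and limits the weight of the point.

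**Conclusion.** The mechanism follows directly from SAP 5.1, 5.1.1 and 9.5.1: a partly used last pack that passes the at-risk filter is credited as 28 days in the primary and method-failure denominators. Taken alone, it always understates the index. The size is small: about 2.5% with exposure ending at last dose, or about 1.4% with the 7-day window credited. Both figures assume uniform stop days and the plan's 80% at-risk rate for last packs. The range over stop-day assumptions is roughly 0 to 5%, well inside the width of the confidence interval.

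A reader might also infer that the reported Pearl Index must be too low overall. The documents do not show this, because the same counting rule credits gap-lengthened cycles as one and nothing is known about their frequency. A net understatement is likely but unproven. The point is worth correcting because the unit of the primary denominator is not properly defined and the remedy is cheap.

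**What to change.** In SAP 9.5.1, define the denominator as the sum over at-risk cycles of cycle length in days divided by 28, using the start and end dates already derived under SAP 5.1. Apply one rule to short and long cycles. Capping long cycles at 28 days would correct in one direction only, and SAP 5.3 treats off-pill gaps as on-treatment time. Keep the conception cycle as one full cycle.

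State whether the last cycle ends at last dose or at last dose plus 7 days (capped at Day 28) to match the numerator window, and report the other choice as a sensitivity analysis. Use the same rule for all method-failure indices.

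The cost is one formula and a small programming change, with no new data. The downside is that the Pearl Index may become slightly less favourable.
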